#### Biomarker Assessments

- In addition to local laboratory testing required for confirmation of eligibility, EGFR mutational status will be assessed in matching blood and formalin-fixed paraffin-embedded (FFPE) tumor tissue collected at screening from each patient by sponsor and/or central laboratory. Tumor tissue from the primary tumor, or an accessible metastatic lesion, will be obtained within 60 days prior to dosing. The corresponding blood specimen will be obtained immediately prior to tumor specimen collection where possible. Dates of tumor samples will be collected. EGFR-mutational status on collected tissue and blood will be assessed by the sponsor.
- Blood will be collected for detection and quantification of mutant EGFR from plasma. Patients will have blood collected during screening, at every cycle Day 1 visit, C1D15 and at disease progression.
- Following disease progression on randomized treatment, patients who provide additional consent will undergo tumor biopsy before subsequent-line therapy is initiated.
- In the Phase 2 part only, in order to be eligible for the crossover portion of the study, erlotinib-treated patients must have an additional biopsy upon progression and within 35 days prior to dosing with CO-1686 to confirm T790M+ status and meet specific eligibility requirements.
- Blood and tissues specimens collected from patients will be used to investigate
  the genetic and transcriptional changes associated with response and resistance
  to erlotinib and CO-1686, for example targeted exon sequencing of 'clinically
  significant' cancer genes using next-generation sequencing technology.
  Extracted genomic deoxyribonucleic acid (DNA) from blood may be compared
  to tumor DNA so that genetic alterations unique to the tumor that may modulate
  response or resistance to EGFR-targeted therapy can be unambiguously
  identified.
- For patients who provide additional consent and are randomized to CO-1686, genomic DNA will be extracted from a blood sample in order to detect genetic polymorphisms in cytochrome P450 (CYP) isozymes and to explore the possible correlation between CYP polymorphism and CO-1686 drug exposure. The extracted genomic DNA from blood may additionally be compared to tumor DNA so that molecular alterations unique to the tumor that may modulate response or resistance to EGFR-targeted therapy can be unambiguously identified.

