## 4.2.3 Exploratory Endpoints

- DCR according to RECIST Version 1.1 as determined by investigator review
- DCR in patients with baseline T790M mutations confirmed by central EGFR mutation assay
- Rate of change in SLD
- Rate of change in tumor volume (measured or modeled)
- InvPFS, ORR, DR, DCR, time-to-treatment failure, and OS in patients who develop PD while on study treatment but continue to receive assigned study treatment with CO-1686 or erlotinib beyond progression
- Concordance of tumor and plasma ctDNA mutational analysis using contemporaneous samples
- Time from randomization to second observed increase over nadir in plasma mutant EGFR ctDNA levels (activating mutation, T790M mutation, either or both)
- Fraction of patients exhibiting disappearance of mutant EGFR ctDNA after initiating treatment with CO-1686
- Change from baseline in other tissue and blood biomarkers associated with the EGFR signaling pathways and relationship with clinical efficacy outcomes

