#### 11.2 Statistical Methods

#### 11.2.1 General Considerations

Quantitative variables will be summarized using descriptive statistics (N, mean, standard deviation, median, minimum, and maximum) and/or frequency and percentages for medically relevant categories. Categorical variables will be presented using frequencies and percentages.

Kaplan-Meier methodology will be used to summarize time-to-event variables. The number of patients with events and the number of censored patients will also be presented. The stratified logrank test will be used to compare the time-to-event distributions between the randomized treatment groups. The same variables used to stratify the randomization will be used in the stratified analyses. In addition, the Cox proportional hazards model will be used to estimate the HR between the randomized treatment groups.

The Fisher's Exact Test will be used to compare frequencies between treatment groups and the t-test will be used for comparing means between treatment groups.

All data will be used to their maximum possible extent but without any imputations for missing data. Results from Phase 2 and Phase 3 will be presented separately and pooled.

All statistical analyses will be conducted with the statistical analysis software (SAS®) system, Version 9.1 or higher.

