#### 11.2.6.3 Tissue and Blood Biomarkers

The change from baseline in tissue and blood biomarkers associated with the EGFR signaling pathway will be summarized with descriptive statistics and the t-test will be used to compare the mean changes between CO-1686 and erlotinib at each scheduled visit.

Both the time from randomization to the first observed increase in plasma mutant EGFR levels and the time from first observed increase in plasma mutant EGFR levels to disease progression will be summarized using Kaplan-Meier methodology.

11.2.6.4 Phase 2 Part Only: Subgroup of Patients that Crossover to CO-1686 from Erlotinib

The subgroup of patients that are initially randomized to erlotinib, experience a RECIST radiographic event of disease progression and test positive for the T790M mutation will be allowed to continue in the study after the initial event of disease progression and crossover to treatment with CO-1686.

The efficacy and safety of CO-1686 will be summarized descriptively in this subgroup of patients (treatment-emergent AEs, invPFS, ORR, DR, DCR and OS).

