## 11.3 Sample Size Considerations

Up to 1,200 patients will be randomized in a 1:1 ratio to receive treatment with CO-1686 or erlotinib. In the Phase 2 part, 200 patients will be randomized 1:1 to either CO-1686 500 mg BID or erlotinib 150 mg QD. In the Phase 3 part, up to 1,000 additional patients will be randomized 1:1 to either CO-1686 500 mg BID or erlotinib 150 mg QD into the single (sponsor)-blinded part of this clinical study.

The primary objective of this study is to estimate the relative improvement in PFS for CO-1686 as compared with erlotinib. The median PFS for erlotinib in this patient population is expected to be approximately 10 months. If CO-1686 has a 13 month median PFS then the HR comparing CO-1686 with erlotinib will be approximately 0.80.

For the Phase 3 part of the study, a total of 640 PFS events will provide approximately 80% power to detect a HR of 0.80 at a 0.025 (1-sided) significance level for the comparison of CO-1686 versus erlotinib.

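### The ctDNA endpoint is defined on the second rise over nadir, but the only specified analysis uses the first rise

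*Combined protocol and SAP*

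**What the plan says.** Section 4.2.3 lists among the exploratory endpoints "Time from randomization to second observed increase over nadir in plasma mutant EGFR ctDNA levels", to be taken for the activating mutation, for T790M, and for either or both. The synopsis gives the same definition, so neither the ordinal nor the nadir reference is a stray slip.

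Section 11.2.6.3 sets out the analysis in one sentence with two clauses. The first clause concerns "the time from randomization to the first observed increase in plasma mutant EGFR levels". The second concerns "the time from first observed increase in plasma mutant EGFR levels to disease progression will be summarized using Kaplan-Meier methodology". Both clauses are anchored on the first rise. Neither mentions nadir or the mutation categories.

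The only other text that bears on the endpoint is the general rule in Section 11.2.1: "Kaplan-Meier methodology will be used to summarize time-to-event variables". That section also names the stratified logrank test for comparing the arms. It defines no events.

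On sampling, the Biomarker Assessments part of the synopsis states: "Patients will have blood collected during screening, at every cycle Day 1 visit, C1D15 and at disease progression".

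**The concern.** A programmer who follows Section 11 as written would produce a time-to-event variable that is not the endpoint in Section 4.2.3, and nothing in Section 11 would prompt anyone to produce the one that is. The two answer different questions. A single upward reading is a weaker signal of molecular progression than a second rise over the lowest level reached.

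Suppression of T790M emergence is part of the study hypothesis in Section 3.3, so the timing of a ctDNA rise is one of the more informative exploratory results. With two definitions on paper, the choice between them could also be made after the ctDNA data have been seen, and the result would then be post hoc.

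**Working it through.** The plan gives no figure for this endpoint, so there is nothing to reproduce. The check is a comparison of texts, an argument about the order of events, and an illustration under stated assumptions.

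**1. The two definitions side by side**

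| Element | Synopsis and Section 4.2.3 | Section 11.2.6.3 |
|---|---|---|
| Which rise | Second | First (both clauses) |
| Reference level | Nadir | Not stated |
| Marker | Activating mutation, T790M, either or both | Mutant EGFR, not split |
| Minimum rise | Not stated | Not stated |
| Rise-to-progression analysis | None | Second clause |

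**2. Order of the events**

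Suppose the first rise over the previous sample occurs at sample j. All earlier samples fell or stayed level, so sample j−1 is the lowest so far. The first rise over the previous sample is therefore also the first rise over the running nadir. A second rise over nadir requires an earlier one, so

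time to first rise ≤ time to second rise over nadir.

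This fails if Section 11.2.6.3 means a rise above baseline. After a deep fall, two rises over nadir could both occur before the level returns to baseline.

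**3. Illustration with no true rise**

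*Assumptions (not from the documents):* log level 0 at C1D1, −2 at C1D15, then flat at −3; independent noise; any positive change counts. *From the plan:* samples at C1D1, C1D15 and Day 1 of each 28-day cycle, i.e. days 0, 14, 28, 56, 84 and so on from first dose.

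While the noise is small compared with the fall, only the plateau samples (day 28 onward) matter, and all k! orderings of k plateau samples are equally likely.

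- First rise by sample k: 1 − 1/k!, since only the strictly falling order has no rise.
- Second rise over nadir by sample k: 1 − [1 + k(k−1)/2]/k!, since at most one sample fails to be a new minimum in 1 + k(k−1)/2 orderings.

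| k | Day | First rise | Second rise over nadir |
|---|---|---|---|
| 2 | 56 | 1 − 1/2 = 50.0% | 1 − 2/2 = 0% |
| 3 | 84 | 1 − 1/6 = 83.3% | 1 − 4/6 = 33.3% |
| 4 | 112 | 1 − 1/24 = 95.8% | 1 − 7/24 = 70.8% |
| 5 | 140 | 1 − 1/120 = 99.2% | 1 − 11/120 = 90.8% |

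Exactly half the series have a first rise by day 56, so that median falls at day 56 or 84. The median for the second rise is day 112. The noise SD does not appear in either formula.

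Simulation of 200,000 series per setting, with SD from 0.05 to 1.0, agrees:

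- First rise: median 56 to 84 days. It was the same visit in every series whether judged against the previous sample or the nadir.
- Second rise over nadir: median 112 days up to SD 0.6, and 84 days at SD 1.0, where noise reaches into the falling phase.
- Second rise counted from sample to sample instead: up to 140 days.

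The overall ranges are therefore 56 to 84 days and 84 to 140 days. If a minimum rise of 0.5 log units is assumed at SD 0.3, the first-rise median moves to day 140 (nadir reference) or 168 (previous-sample reference).

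**4. If spurious rises are rare**

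Take 10 monthly samples, in line with Section 11.3: "The median PFS for erlotinib in this patient population is expected to be approximately 10 months". Let each sample have an assumed independent chance p of a spurious rise.

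- At least one: 1 − (1−p)^10
- At least two: 1 − (1−p)^10 − 10p(1−p)^9

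| p | At least one | At least two |
|---|---|---|
| 0.02 | 18.3% | 1.6% |
| 0.05 | 40.1% | 8.6% |
| 0.10 | 65.1% | 26.4% |
| 0.20 | 89.3% | 62.4% |

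**The case against.** The strongest reply is that Section 11.2.1 already applies Kaplan-Meier methods to every time-to-event variable, so the Section 4.2.3 endpoint could be analysed under that rule and Section 11.2.6.3 merely adds two further analyses. This stands in part. A reader might infer that the defined endpoint is barred from analysis or would never be analysed, and the documents do not say that. They do leave it without a specified analysis, while the only named ctDNA time-to-event analysis uses another event.

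Three stronger readings are tempting and do not hold:

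- **Dropping the nadir reference makes the first rise noisier.** With no minimum rise, a first rise over the previous sample and a first rise over the nadir are the same event (step 2).
- **The gap between the medians measures assay noise.** It barely depends on the assumed SD. It comes from counting any positive change on a monthly grid. The model also leaves out undetectable plateaus, where tied readings give no rise, although Section 4.2.3 expects mutant ctDNA to disappear in some patients.
- **The second-rise rule protects against noise.** With no true rise it still fires, at a median of 84 to 140 days in the model. It delays false events without preventing them, and the documents never say it was chosen for that purpose.

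It is also fair to say that little depends on this now. Development has been discontinued, and the Extension Phase schedule (Appendix D, Table 4) has no ctDNA draw. Samples already collected can still be analysed.

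**Conclusion.** Wrong as written, with low severity. The endpoint in the synopsis and Section 4.2.3 and the analysis in Section 11.2.6.3 name different events, and no other text reconciles them.

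The direction is firm if a rise is judged against the previous sample or the nadir: the analysed event is never later than the defined one. It is not firm if a rise above baseline was meant, and Section 11.2.6.3 does not say which. The size of the shift cannot be derived from the documents, because they give neither assay precision nor a minimum rise. The day ranges and percentages above are illustrations under a model with no true rise, and are not predictions for this trial. The effect on any difference between the arms is not established either.

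The endpoint is exploratory. The primary invPFS analysis, alpha and sample size are unaffected.

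**What to change.** In the first clause of Section 11.2.6.3, make the analysed endpoint the time from randomization to the second observed rise over nadir, reported for the mutation categories in Section 4.2.3. Keep the time to first rise, and the time from first rise to progression, as labelled supportive analyses. The latter is a lead-time question with no counterpart in Section 4.2.3, so it should not be rewritten to match it.

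The same edit is a natural place to state the reference level for the first rise, any minimum rise that counts, and how patients without an event are censored. The documents offer no basis for a particular minimum rise, so that value would have to come from the assay's own performance data.

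The cost is an edit to one sentence and one additional derived variable. It needs no new samples or visits. It should be settled before ctDNA results are examined by arm.

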	The objectives of Study CO-1686-022 (known as TIGER-1) are to compare the antitumor efficacy of oral single-agent CO-1686 to erlotinib when administered as a first-line targeted treatment to patients with EGFR-mutated, advanced/metastatic NSCLC and to assess the safety and tolerability of CO-1686 in this population. Efficacy will be measured primarily by PFS. Secondary efficacy measures will include patient reported outcomes (PRO), RECIST response rate, duration of response (DR), and OS (although control arm crossover may limit the utility of the OS data). Relative benefit of CO-1686 versus erlotinib will specifically be studied in de novo T790M+ patients. This study will also compare the treatment effects of CO-1686 and erlotinib on surrogate markers that may be predictive of disease progression and evaluate possible predictive biomarkers.
Planned Number of Patients	In the Phase 2 part, 200 patients will be randomized 1:1 to either CO-1686 500 mg BID or erlotinib 150 mg once daily (QD).  In the Phase 3 part, up to 1,000 additional patients will be randomized 1:1 to either CO-1686 500 mg BID or erlotinib 150 mg QD into a single (sponsor)-blinded part of this clinical study.
Planned Number of Sites	Approximately 95 investigative sites will be open globally.

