# 4.1.3 Exploratory Objectives

- To compare DCR of oral single-agent CO-1686 with that of erlotinib when administered as a first-line targeted treatment in patients with advanced/metastatic NSCLC whose tumors have EGFR-activating mutations
- To assess DCR in patients with baseline T790M mutations based on central allele-specific PCR EGFR mutation assay
- To compare kinetics of tumor growth between treatment arms measured by rate of change in sum of the longest diameters of target lesions (SLD) or rate of change of estimated or measured assessments of tumor volume
- To compare efficacy between treatment arms in patients with baseline T790M+ disease, detected using an ultra-sensitive research assay
- To compare the effect between treatment arms in patients who develop progressive disease (PD) while on study treatment but continue to receive assigned study treatment with CO-1686 or erlotinib beyond progression

- To evaluate concordance of EGFR mutation detection between patient tissue and plasma and to assess CO-1686 or erlotinib mediated alterations in levels of EGFR mutation detected using circulating tumor DNA (ctDNA) obtained from patient plasma
- To explore tissue and blood-based biomarkers that may be predictive of response or primary resistance to CO-1686 or erlotinib and investigate mechanisms of acquired resistance to treatment with CO-1686 or erlotinib using patient tumor tissue and blood samples

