- Blood sampling for biomarker/EGFR mutational testing and exploratory research will be collected at screening (prior to biopsy, where possible); predose on C1D1, C1D15, then at every study Cycle visit Day 1 (every 28 ± 3 days), and at the End-of-Treatment Visit.
- Blood for CYP evaluation to be collected predose on Day 1 (Cycle 1) for patients randomized to receive CO-1686 who have signed optional consent.

Table 9-1: Schedule of Assessments in Phase 2 (Before Crossover) and in Phase 3 (Cont.)

	Scre	ening					Follow-up (Every 8 ±				
Procedure b	≤35 Days Prior to Cycle 1 Day 1	≤14 Days Prior to Cycle 1 Day 1	Cycle 1 Day 1 (C1D1) c	Cycle 1 Day 4 ± 1 Day d	Cycle 1 Day 8 ± 1 Day d	Cycle 1 Day 15 ± 1 Day d	Cycle 2 Day 1 (28 ± 3 days after C1 D1)	Cycle 2 Day 15 ± 1 Day d	Cycle 3 + Every 28 ± 3 Days	End-of- Treatment t 28 Days ±7 Days After Last Dose	1 weeks for scans, every 3 months ± 7 days for survival and subsequent therapy starting at End-of-Treatment)

Patients will be monitored for AEs from the time the first dose of CO-1686 or erlotinib is administered through 28 days after the last dose (ongoing SAEs at the time of the End-of-Treatment Visit will be followed until resolution or stabilization). Study procedure-related AEs that occur after signing of the ICF and before administration of CO-1686 or erlotinib will also be collected. On C1D1 AEs will be monitored pre- and postdose.

<sup>q Patient diaries should be collected and reviewed for compliance.

Taken in triplicate as 10 second tracings > 2 min apart anytime during screening, 5 to 10 minutes prior to dosing on C1D1, C1D8, C1D15, then at every study cycle visit during treatment (occurring at 28 ± 3 days intervals) and at end-of-treatment, any time after treatment is discontinued.

S QOL questionnaires (EORTC QLQ-C30, EORTC QLQ-LC13, the DLQI, and the EQ-5D) will be collected at screening, predose on C1D1 then every 8 ± 1 weeks for the first 6 months (Day 1 of Cycles 3, 5, 7, inclusive). After Cycle 7, questionnaires will be collected every 12 ± 1 weeks (Day 1 of Cycles 10, 13, 16, etc.) and at end-of-treatment.

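### The time from first ctDNA increase to progression is conditional on an increase and, for an uninformative marker, returns only residual PFS; a time-dependent analysis should accompany it (exploratory, low priority)

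*Combined protocol and SAP*

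**What the plan says.** Section 11.2.6.3 (Tissue and Blood Biomarkers) plans two Kaplan-Meier summaries for plasma mutant EGFR. One runs from randomization to the first observed increase. For the other, "the time from first observed increase in plasma mutant EGFR levels to disease progression will be summarized using Kaplan-Meier methodology".

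The section sets no minimum size and no confirmation rule for an increase. It does not say who enters the second summary, or what happens to patients who progress without an increase or whose first increase comes at or after progression. It plans no comparator and no landmark or time-dependent analysis.

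Blood is drawn at screening, "predose on C1D1, C1D15, then at every study Cycle visit Day 1 (every 28 ± 3 days), and at the End-of-Treatment Visit". The biomarker part of the Synopsis adds a draw at disease progression, and Section 5.1.2 continues biomarker sampling in patients treated beyond progression. Section 4.2.3 defines the related endpoint differently, as the second increase over nadir, timed from randomization. Its only mention of a relationship with clinical outcome concerns other biomarkers and gives no method.

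The Synopsis says the study will compare treatment effects on "surrogate markers that may be predictive of disease progression". The ctDNA objective in Section 4.1.3 is "To evaluate concordance of EGFR mutation detection between patient tissue and plasma and to assess CO-1686 or erlotinib mediated alterations in levels" of EGFR mutation in plasma.

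**The concern.** Anyone shown a median time from ctDNA increase to progression will tend to read it as the warning the marker gives. The interval cannot carry that meaning. Progressors without a prior increase have no time origin, and a first increase after progression would give a negative time that Kaplan-Meier cannot use. Both groups fall out without being counted as failures of the marker.

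For those who remain, an increase that occurs for reasons unrelated to progression is just an arbitrary point on the PFS time axis, and the interval from it is residual PFS. A noisy marker can therefore show a longer interval than one that really rises shortly before progression. If the summary is shown by arm, the PFS difference would reappear as an apparent ctDNA difference.

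**Working it through.** **Inputs.** Section 11.3: "The median PFS for erlotinib in this patient population is expected to be approximately 10 months", and "If CO-1686 has a 13 month median PFS then the HR comparing CO-1686 with erlotinib will be approximately 0.80". Section 9: ctDNA draws at Day 15, then every 28 days; scans every 8 weeks. Assumed, because the documents give no figure: the shape of the PFS hazard, the rate of false increases per draw, and that PFS events are progressions.

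**1. The plan's own figure.** Section 11.3 says "a total of 640 PFS events will provide approximately 80% power to detect a HR of 0.80 at a 0.025 (1-sided) significance level". Schoenfeld: 4 × (1.960 + 0.842)² / (ln 0.80)² = 631 events. Freedman: (1.80/0.20)² × (1.960 + 0.842)² = 636. Power with 640 events is 80.6%. The figure reproduces. The ratio of medians, 10/13 = 0.77, is close to the stated 0.80, so the planning figures fit a constant hazard.

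**2. Uninformative marker, closed form.** Take Weibull PFS with median M and shape k. For a trigger at time s that is unrelated to progression, the residual median m solves S(s + m)/S(s) = 0.5:

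m = (s^k + M^k)^(1/k) − s

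With k = 1 (constant hazard), m = M for every s: 10 months on erlotinib and 13 on CO-1686. For the arms pooled 1:1, solving ½·2^(−t/10) + ½·2^(−t/13) = ½ gives 11.4 months.

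With a rising hazard and M = 10:

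| Shape k | Trigger at 28 days (s = 0.92 months) | Trigger at 168 days (s = 5.52 months) |
|---|---|---|
| 1 | 10.0 | 10.0 |
| 1.25 | 9.5 | 8.1 |
| 2 | 9.1 | 5.9 |

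**3. Simulation on the actual draw and scan schedule, uninformative marker.**

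- Every upward tick counts, constant hazard, erlotinib: 94% of patients have an increase before progression and the median interval is 10.0 months. With 8-week scans, 99.5% have one on or before progression, the median is 10.1 to 10.6 months, and 1.6% of intervals are exactly zero.
- Same rule on CO-1686: about 13 months.
- Rising hazard (shape 1.25 to 2), erlotinib: 9.2 to 9.6 months when every tick counts (10.1 with scans), and about 6.4 to 9.2 months if false increases are rarer (assumed 5% to 20% per draw).
- Data cut at 70% events, constant hazard: with an assumed 10% false-increase rate, 66% of patients contribute, 41% of progressors are absent and the median is about 10 months. At 30%, 92% to 93% contribute, about 11% of progressors are absent and the median is again about 10 months.
- Using the second increase instead of the first: 9.2 to 10.1 months with scans.

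**4. A marker that carries information.** Suppose it rises about 2 months before progression in 70% of patients. The same summary gives about 1.5 to 3 months, depending on whether the 2 months are counted back from true or scan-detected progression.

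**5. The alternative on simulated data.** With increase as a time-dependent covariate (60 trials of 500 patients), the uninformative marker gave HR 1.02, with p < 0.05 in 5% to 7% of runs. A marker mixing real and false increases gave HR 5.1, with p < 0.05 in every run. For a marker with real increases only, the model did not converge, because prediction was near perfect.

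**The case against.** The case for leaving the section alone has real substance.

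- The analysis is exploratory and descriptive, with no test or decision attached. This stands and sets the priority.
- The documents never call the interval a lead time. The Synopsis sentence concerns treatment effects on markers and does not name ctDNA, and Section 4.1.3 covers concordance and changes in level. A reader might infer that the plan claims to test ctDNA as a surrogate; the text does not support that.
- The restriction to patients with a prior increase is not written. It follows from the definition, on which the plan is silent. A reader might also call the interval positive by construction. That is too strong: blood drawn at progression allows zeros.
- A reader might blame the 10 months on the exclusion of patients without an increase. That is not the main cause. When every tick counts, almost everyone enters. The size comes from an increase with no threshold and from residual PFS.
- The companion curve from randomization to first increase would partly expose a marker that fires early. At a 30% false rate, 0.7² = 0.49 of patients are still without an increase at Cycle 2 Day 1 (0.9 months). At 10%, 0.9⁷ = 0.48 are without one at Cycle 7 Day 1 (5.5 months). Section 11.2.1 also requires event and censored counts. This helps, but neither output relates the increase to progression, and the counts do not separate progressors without an increase from patients still at risk.
- Development has stopped, enrollment is closed, and the Extension Phase schedule in Appendix D has no ctDNA draw. Urgency falls accordingly, although Section 11.2.6.3 still governs samples already collected.

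**Conclusion.** The point holds in limited form. Taken alone, the interval from first increase to progression cannot show whether a ctDNA increase says anything about progression. For an unrelated marker it returns about 10 months on erlotinib and 13 on CO-1686 under constant hazard, a 3-month gap between arms that is only the PFS gap. On erlotinib it returns roughly 6 to 10 months under a rising hazard. A marker with a real 2-month rise would show only 1.5 to 3 months.

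These sizes rest on the Section 11.3 medians, assumed hazard shapes, assumed false-increase rates and a marker that is pure noise. They are benchmarks, not predictions for the assay used here. They do not show that the trial's ctDNA data are noise, or that longer intervals always mean a worse marker. The primary endpoint and the 640 events are untouched, so priority is low.

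**What to change.** In Section 11.2.6.3:

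1. Define an increase (reference value, minimum size or confirmation, first or second) and reconcile it with Section 4.2.3.
2. Keep the Kaplan-Meier interval as description only, labelled as conditional on an increase on or before progression.
3. Report, by arm, the number and proportion of progressors with no prior increase.
4. Add a Cox model for invPFS in patients with ctDNA data, with increase as a time-dependent covariate based only on samples taken before progression. Stratify by EGFR mutation and territory, and give the HR and 95% CI overall and by arm. Name a landmark analysis as the fallback if the model does not converge.

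Cost: some wording and one more exploratory model on data already collected. The interval will read less favourably than it would alone.
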